#### Group VCI Sessions

Using the UTN-supported Acano platform, women will attend weekly, 1-hour videoconference sessions with 4–5 other participants (maximum  $n = 6$ ), for a total of 10 sessions: one initial session for getting acquainted with one another and the program, eight sessions for engagement in the VCI intervention, and a follow-up “reunion” 6–8 weeks after the last session. Members of the Latina community will be enrolled in study groups that will include 15 minutes of extra mental health content, based on recommendations from the focus groups done in the community and their needs (actual intervention content will not be altered, just additional mental health background will be included). Participants will attend each session using their own Internet connection and electronic device (computer, laptop, electronic tablet, smart phone) to connect to Acano. Alternatively, participants can connect via the Internet without video, or as a last resort can simply call in by telephone landline or basic mobile phone. The intervention is a standardized and manualized program called UPLIFT (Using Practice and Learning to Increase Favorable Thoughts), developed and evaluated by [name]. UPLIFT is an 8-week group intervention based on CBT and MBP, therapies with demonstrated effectiveness in the prevention and treatment of depression. Originally developed as an online and telephone-based approach, we have adapted and piloted the program for videoconference use in a pregnant population. Our revised telehealth approach has several advantages over conventional in-person therapies, including (1) improved accessibility to therapy among working, low-income, and rural-dwelling mothers, and those with time, childcare, and transportation barriers; (2) the ability to develop a supportive community among other mothers of similar risk status and life circumstances; (3) the ability for women to build an effective skill set for the prevention and treatment of depression that can last a lifetime; (4) the addition of nonverbal communication between group participants and the facilitator when videoconferencing is used; and (5) sufficient time to acquire and practice Mindfulness-Based Cognitive Behavioral Therapy skills early in pregnancy, prior to baby's arrival and the postpartum period, when the risk of depression is highest. After the 8-week intervention, a cohort “reunion” will be held approximately 6–8 weeks after the last session. The approach just described was developed based on the strong recommendations of participants in our pilot studies, including the initial pre-UPLIFT meeting

and post-UPLIFT “reunion.” Women will begin VCI sessions no later than 20-weeks gestational age, with completion no later than 36 weeks gestational age.

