
## Purpose and Objectives

---

The study will evaluate the effectiveness of a videoconference intervention (VCI) to reduce perinatal depression symptoms (PDS) and anxiety (a highly co-morbid condition) by conducting a randomized controlled trial among women experiencing mild to moderate PDS, as measured by the Edinburgh Postnatal Depression Scale (EPDS). Furthermore, we propose to evaluate differences in response to the VCI between subgroups of childbearing women; Hispanic and North European Descent populations, and rural and urban-dwelling.

Specific aims of the study include:

Aim 1: Evaluate the effectiveness of a VCI to reduce PDS and anxiety, as measured by EPDS and Generalized Anxiety Disorder-7 Item (GAD-7) scores across pregnancy and the postpartum. Methods: Pregnant women of all gestational age up to 6 months postpartum (n = 240) who screen positive for mild to moderate PDS (EPDS scores 9–20) will be randomly assigned to VCI or AC for eight weeks. Both groups will continue with standard care as directed by their primary/prenatal care providers. The EPDS and GAD-7 will be administered at three time points during pregnancy and at 2, 4, and 6 months postpartum. Hypothesis: Women participating in the VCI will have significantly lower post intervention EPDS and GAD-7 scores across pregnancy and postpartum than women in the AC group.

Secondary Aim 1: Explore differences in the effectiveness of the VCI to reduce PDS and anxiety across women who enroll at different stages of their pregnancy or postpartum periods.

Aim 2: Evaluate the interaction of the VCI with specific subgroups: ethnicity (Hispanic, North European descent), geographic location (rural, urban), and the outcome of PDS as measured by EPDS and GAD-7 scores across pregnancy and postpartum. We will oversample in Hispanic and rural populations to ensure sufficient representation from diverse groups. Hypothesis: Women will demonstrate differences in EPDS and GAD-7 scores across pregnancy and postpartum, dependent on their study group membership.

Secondary Aim 2: Explore an additional subgroup analysis, namely between those who are and who are not taking medication at the time of screening.

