**Inclusion Criteria:**

The study will include women 18 years of age and older who, at time of enrollment (1) have a viable pregnancy or have given birth within the previous 6 months, (2) have an Edinburgh Postnatal Depression Scale (EPDS) score of 9–20; (3) are English- or Spanish-speaking; and (4) are attending a collaborating prenatal or public health clinic associated with the University of Utah or Utah Department of Health.

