#### Stratified Randomization Into Study Groups

After consenting to participate, women will be assigned by computer-generated randomization by two different stratifications (Hispanic/NED and Urban/Rural) to one of two study groups: Videoconference intervention (VCI) or Attention Control. Both groups will continue with standard of care as directed by their prenatal care provider. After randomization, the participant will receive study information pertinent to her specific study group, by mailed hard copy and/or emailed electronic document. Enrollment and randomization will continue until the following enrollment goals are met.

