#### VCI Participants

A study team member will contact the participant by telephone and/or email to determine which group start date works best for her and to schedule a time for technology testing and instruction.

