### Attention Control (AC) Group

Women who are randomized into the AC will participate in an 10-week education program delivered by group videoconference platform supported by UTN. The education program is manualized and designed to enhance participant knowledge related to pregnancy, childbirth, newborn care, and feeding, or parenting young babies. All participants in the AC group will receive a mailed hard copy and/or emailed electronic packet (participant’s choice) that includes topical education, which includes information about perinatal depression and mood disorders (e.g., anxiety and obsessive-compulsive disorder, postpartum psychosis), interpretation of EPDS scores, common therapies for PD, local resources for obtaining therapies, and encouragement to discuss their EPDS scores with their prenatal care provider. This approach provides a control group that reduces bias as much as possible, and most closely reflects an optimal care level that includes screening and patient education for all pregnant and postpartum women.

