### **Procedures performed for research purposes only:**

Group Videoconference Intervention Sessions (UPLIFT Manualized Program): All sessions will be facilitated by a credentialed mental health professional specifically trained in the UPLIFT program. Each 1-hour session will include a check-in, instruction, skill building, discussion. The facilitator will use an UPLIFT manual as the outline for each specific session of the 8-week series. Each participant will also receive the UPLIFT manual (print and/or electronic document), which contains details and resources for each session. Sessions will focus on increasing knowledge about depression and pregnancy, CBT, and MBP. Participants will learn and practice skills related to CBT and mindfulness, and engage in discussions and group exercises for each session's main topic. Topics include thought monitoring, identify distortions in thoughts, self-esteem, identification of problems, goal setting, and achieving support. Exercises include relaxation; body scan; progressive muscle relaxation; attention to breath, sights, and sounds; and meditation. Each week, participants will be provided with

recommendations for between-session practices, which will be discussed at the beginning of the next class.

Attention Control Group (delivered by group videoconference platform): The education program for women  $\geq 32$  weeks gestation is manualized and designed to enhance participant knowledge related to pregnancy, childbirth, newborn care, and feeding. The education program for women  $> 32$  weeks gestation is designed to enhance knowledge related to parenting and young babies. All participants in the AC groups will receive a mailed hard copy and/or emailed electronic packet (participant's choice) that includes topical education, which will also include information about perinatal depression and mood disorders (e.g., anxiety and obsessive-compulsive disorder, postpartum psychosis), interpretation of EPDS scores, common therapies for PD, local resources for obtaining therapies, and encouragement to discuss their EPDS scores with their prenatal care provider.

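### The rule that VCI sessions begin by 20 weeks' gestation contradicts eligibility at any gestation up to 6 months postpartum, and it has no counterpart before randomisation or in the AC arm

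*Combined protocol and SAP*

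**What the plan says.** **The timing limit.** Group VCI Sessions ends with: "Women will begin VCI sessions no later than 20-weeks gestational age, with completion no later than 36 weeks gestational age". The sentence names VCI sessions only.

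**Who is enrolled.** Aim 1 (Purpose and Objectives) randomises to VCI or AC a population described as "Pregnant women of all gestational age up to 6 months postpartum (n = 240" in total). Inclusion Criteria requires that women "have a viable pregnancy or have given birth within the previous 6 months". Neither Inclusion Criteria nor Exclusion Criteria contains a gestational cut-off. Secondary Aim 1 explores effectiveness "across women who enroll at different stages of their pregnancy or postpartum periods".

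**Order of events.** Enrollment, and the recruitment section before it, have gestational age confirmed from the health record around consent. Then, under Stratified Randomization Into Study Groups: "After consenting to participate, women will be assigned by computer-generated randomization by two different stratifications (Hispanic/NED and Urban/Rural" being the two factors). Only after allocation does staff contact the VCI participant "to determine which group start date works best for her" (VCI Participants).

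**The AC arm.** Its programme covers "pregnancy, childbirth, newborn care, and feeding, or parenting young babies" (Attention Control (AC) Group). Procedures performed for research purposes only splits the AC content at 32 weeks, and one of the two programmes "is designed to enhance knowledge related to parenting and young babies". No start or completion limit is given for AC.

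**Outcome times.** Aim 1 places three EPDS and GAD-7 assessments before birth and three after it, at 2, 4 and 6 months. Participant-Completed Questionnaires, and the matching text under Procedures performed for research purposes only, place T1 at enrolment, T2 after session 9 (end of intervention), and T3 to T6 at 2, 4, 6 and 8 months after that, with no reference to the date of birth.

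**The concern.** The limit and the eligibility rules cannot both be followed. A woman at 24 or 36 weeks satisfies every written entry criterion and can be allocated to VCI, yet by then she cannot start in time. Read literally, the same holds for a woman who has already given birth.

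The limit is one-sided and acts after allocation. A window applied to both arms before randomisation would only change who is in the trial. A window applied to one arm after randomisation changes what allocated women receive in that arm alone. Under the planned intention-to-treat analysis those women still count as VCI, so the estimated effect is pulled down. Secondary Aim 1 would also be left without treated women at the stages the limit excludes.

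The outcome calendar matters less. The trial is powered on Intervention x Time, and the documents give two meanings of time: time relative to birth, and time since the end of the sessions.

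**Working it through.** The plan gives no figure on this point to reproduce, so the check sets the texts side by side and adds simple calendar arithmetic.

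**1. Is the limit coherent in itself?** Group VCI Sessions has one introductory session and eight weekly intervention sessions, then a reunion 6 to 8 weeks after the last session.
- Start at 20 weeks: session 9 falls at 20 + 8 = 28 weeks.
- Reunion: 28 + 6 = 34 to 28 + 8 = 36 weeks.

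This meets the 36-week completion limit exactly. The sentence is therefore consistent for a trial that enrols only in early pregnancy. It does not fit the trial described elsewhere.

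**2. Who can comply?** Latest compliant enrolment = 20 weeks minus the lead from enrolment to session 1. The lead is not stated, so I assume 1 to 6 weeks: 20 - 1 = 19 weeks down to 20 - 6 = 14 weeks. Later pregnant enrollees cannot comply, nor, read literally, can any postpartum enrollee.

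**3. Does anything stop such a woman before allocation?**
- Gestational age is confirmed before randomisation, but with no 20-week criterion attached.
- Inclusion Criteria and Exclusion Criteria have none.
- Randomisation is stratified by ethnicity and residence only.
- The VCI start date is chosen after allocation.
- The facilitator meeting, also after allocation, screens for mental health concerns and names no gestational criterion.

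**4. Size of the dilution.** Let w be the share of the VCI arm held back and d the effect in women who receive VCI. If held-back women fare as AC women do (an assumption), the intention-to-treat effect is (1 - w) x d. It runs from d at w = 0 to nothing at w = 1. The documents give no enrolment distribution by stage, so w cannot be narrowed and I claim no power loss.

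**5. Outcome calendar.** Assumptions: weekly sessions, birth at 40 weeks, 4.35 weeks per month. T2 = start + 8 weeks, and T3 to T6 follow at 8.7, 17.4, 26.1 and 34.8 weeks after T2.

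| Sessions start | T2 | T3 | T4 | T5 | T6 |
|---|---|---|---|---|---|
| 20 weeks | 28 weeks | 36.7 weeks | 1.2 months after birth | 3.2 | 5.2 |
| 32 weeks | birth | 2.0 months after birth | 4.0 | 6.0 | 8.0 |
| 6 months after birth | 7.8 months after birth | 9.8 | 11.8 | 13.8 | 15.8 |

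For T4 to T6 to fall at 2, 4 and 6 months after birth, the start must satisfy start + 8 + 17.4 = 40 + 8.7, so start = 23.3 weeks. That is already past the 20-week limit, and T3 then falls at birth (23.3 + 8 + 8.7 = 40). No arithmetic is needed for postpartum enrollees: they cannot supply any assessment in pregnancy.

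**The case against.** The strongest reply is that the 20-week sentence is stale. Aim 1, Secondary Aim 1, Inclusion Criteria, the AC content and the comparison of partum groups in the analysis section all describe a trial open to all stages. Staff faced with one stray sentence would probably ignore it rather than withhold VCI from women already randomised. This is plausible, and it makes the harm conditional. It does not remove the contradiction: the sentence is current text and binds anyone who follows the protocol.

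A reader might infer four stronger things that the documents do not support.
- *That women past 20 weeks are being denied VCI.* Nothing shows that the limit is enforced.
- *That there is no check of gestation before randomisation.* There is one; it lacks a stated cut-off.
- *That Secondary Aim 1 fails altogether.* If the limit is meant for pregnant women only, postpartum enrollees are unaffected and only later-pregnancy stages are hit.
- *That the two calendars bias the comparison between arms.* Both arms share T1 to T6.

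On the calendar, it is also fair to say that the two operational sections agree with each other, that Aim 1's sentence is the outlier, and that the analysis section speaks of up to six time points and so does not demand six from every woman. That makes the conflict minor. It does not say which clock defines time.

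**Conclusion.** The plan is wrong as written. The VCI timing sentence contradicts the eligibility rules and Secondary Aim 1, and the AC arm has no equivalent. If the sentence is followed, eligible women past 20 weeks (and, read literally, postpartum women) can be randomised to VCI and then not be allowed to start. The intention-to-treat effect would be diluted by an amount the documents do not allow to be computed, and Secondary Aim 1 would be undercut for at least the later-pregnancy stages. The contradiction rests on the text alone; the harm depends on the sentence being applied. It should be fixed.

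The outcome-time conflict is secondary and minor. It affects how Intervention x Time is interpreted. The dates in the table depend on the stated assumptions, but the impossibility for postpartum enrollees does not.

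**What to change.** Delete the timing sentence at the end of Group VCI Sessions, so that VCI is open to every eligible woman, as AC is. Rewrite the outcome-time sentence in Aim 1 to the questionnaire schedule: enrolment, after session 9, then 2, 4, 6 and 8 months later. Intervention x Time then has one time axis.

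Both changes cost amendment wording only, with no new data and no change to the target of 240. If enrolment has begun, the sponsor should state whether anyone allocated to VCI was held back under the sentence.

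If a gestational window is wanted on clinical grounds, it must be an eligibility criterion applied before randomisation to both arms. That is not a wording change: it narrows the population, bears on recruitment of 60 women in each of the four ethnicity-by-residence cells, and removes stages from Secondary Aim 1.

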### UPLIFT Manualized Program

All sessions will be facilitated by a credentialed mental health professional specifically trained in the UPLIFT program. Each 1-hour session will include a check-in, instruction, skill building, and discussion. Latina participants will have 15 minutes extra content to discuss mental health more in depth as part of the intervention group, based on feedback we received, which will not alter the actual intervention content itself. The facilitator will use an UPLIFT manual as the outline for each specific session of the 8-week series. Each participant will also receive the UPLIFT manual (print and/or electronic document), which contains details and resources for each session. Sessions will focus on increasing knowledge about depression and pregnancy, CBT, and MBP. Participants will learn and practice skills related to CBT and mindfulness, and engage in discussions and group exercises for each session’s main topic. Topics include thought monitoring, identifying distortions in thoughts, self-esteem, identification of problems, goal setting, and achieving support. Exercises include relaxation; body scan; progressive muscle relaxation; attention to breath, sights, and sounds; and meditation. Each week, participants will be provided with recommendations for between-session practices, which will be discussed at the beginning of the next class.

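### The 15 minutes of extra content described for Latina women in the VCI arm is fully aliased with Aim 2's VCI-by-ethnicity interaction, so that interaction cannot be attributed to ethnicity

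*Combined protocol and SAP*

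**What the plan says.** Two places in the combined protocol and SAP describe the addition. Group VCI Sessions says: "Members of the Latina community will be enrolled in study groups that will include 15 minutes of extra mental health content". UPLIFT Manualized Program says: "Latina participants will have 15 minutes extra content to discuss mental health more in depth as part of the intervention group". The first adds the qualification that "actual intervention content will not be altered, just additional mental health background will be included", and the second makes the same point. Neither says how often the 15 minutes are given.

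Procedures performed for research purposes only repeats the UPLIFT description without the addition: "Each 1-hour session will include a check-in, instruction, skill building, discussion".

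For the control arm, Attention Control (AC) Group says: "The education program is manualized and designed to enhance participant knowledge related to pregnancy, childbirth, newborn care, and feeding, or parenting young babies". Neither description of the AC programme mentions extra content for Latina women. The Latina Focus Groups section does say that feedback was sought on tailoring both arms, but no resulting AC addition is described.

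Aim 2, under Purpose and Objectives, is to "Evaluate the interaction of the VCI with specific subgroups: ethnicity (Hispanic, North European descent", with geographic location as the second factor. The enrollment goals give 60 Latina women and 60 NED women to each arm. Neither data-analysis section mentions the extra content or limits how the ethnicity result will be read.

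**The concern.** Aim 2 asks whether the VCI works differently in Hispanic and NED women, and treats the VCI as one intervention. As described, Latina women in VCI receive something more than NED women in VCI, on the subject that the outcomes measure. A larger Latina effect could then come from the added content, from a real difference in response, or from both. A null interaction could hide a smaller response to UPLIFT that the added content offsets.

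Half of the 240 enrollment places are set aside for Latina women, and ethnicity is one of the two subgroup factors named in Aim 2. An unqualified report could credit or blame ethnicity for what was a difference in the package.

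**Working it through.** The plan states no figure on this point, so there is none to reproduce. The check has three parts.

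**1. Can the two effects be separated?** Let τ be the VCI effect in NED women, δ the true change in that effect for Latina women, and γ the effect of the extra content. With AC means μ_N and μ_L, and the content in Latina VCI only:

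| Cell | Women (goal) | Extra content | Mean |
|---|---|---|---|
| NED, AC | 60 | no | μ_N |
| NED, VCI | 60 | no | μ_N + τ |
| Latina, AC | 60 | none described | μ_L |
| Latina, VCI | 60 | yes | μ_L + τ + δ + γ |

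- Interaction: (τ + δ + γ) − τ = δ + γ. There is one estimable quantity and two unknowns.
- A design matrix with columns for intercept, arm, ethnicity, arm × ethnicity and extra content has five columns and rank 4, because the last two columns are identical. A larger sample does not change this.
- Pooled effect with equal cells: [τ + (τ + δ + γ)]/2 = τ + (δ + γ)/2. This is a valid randomized effect of the mix delivered.
- The urban/rural interaction is not aliased in this way, because the enrollment goals balance ethnicity within location.

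**2. How much extra contact?** The inputs are 15 minutes (quoted above), a base session of one hour ("Each 1-hour session will include a check-in, instruction, skill building, and discussion"), and "eight sessions for engagement in the VCI intervention", within 10 sessions in all. I assume the 15 minutes are added to the hour.

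- Every session: 15/60 = 25% more. That is 8 × 15 = 120 extra minutes over eight sessions, or 10 × 15 = 150 over ten.
- Once only: 15/(8 × 60) = 15/480 = 3.1% more over the eight sessions.

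**3. What could this do to the interaction test?** This is an illustration with assumed values of γ and with δ = 0. The SD of 5 and the correlation of 0.3 come from the Data Analysis section, and 60 per cell from the enrollment goals. I also assume independent women, no clustering by session group, a two-sided 0.05 test and a normal approximation.

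- One time point: SE = √(4 × 5²/60) = √1.667 = 1.29.
- Mean of the five post-baseline measures: variance per woman = 25 × (1 + 4 × 0.3)/5 = 11, so SE = √(4 × 11/60) = 0.86.
- Rejection probability = 1 − Φ(1.96 − |γ|/SE) + Φ(−1.96 − |γ|/SE).

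| Assumed effect of extra content (EPDS points) | One time point | Mean of five |
|---|---|---|
| 0 | 5% | 5% |
| 0.5 | 6.7% | 9.0% |
| 1 | 12.1% | 21.5% |
| 2 | 34.1% | 64.6% |

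The power calculation uses 192 women in total. With 192/4 = 48 per cell, the 1-point row becomes 10.7% and 18.1%.

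**The case against.** The strongest reply is that this is legitimate tailoring of an unchanged intervention. The documents say that the UPLIFT content is not altered, each woman is randomized within her ethnic stratum, and the interaction is a sound contrast of what was delivered. Aim 2's hypothesis does not name ethnicity as a cause. Ethnicity is not randomized, so removing the 15 minutes would not isolate a causal effect of ethnicity either. All of this stands, and it is why the point is limited to interpretation. It does not remove the aliasing: added mental health discussion is still added content, given to one ethnic group in one arm.

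The plan will explore dose of participation and will record a random selection of sessions for fidelity. Both help to describe delivery. Neither separates δ from γ, because the addition is fixed by ethnicity and arm.

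A reader might infer three stronger claims that the documents do not support:

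- **The content is given at every session.** The placement directly after the description of the 1-hour session suggests this, but no frequency is stated. Nor do the documents give any basis for scaling the VCI benefit to minutes of contact.
- **Latina AC women receive no matching time.** The text is silent, which is weaker evidence. Feedback was sought on both arms, the randomization section uses the term study groups for VCI and AC alike, and no AC session length is given, so time matching cannot be judged for anyone. The VCI heading and the words on the intervention group favour the VCI-only reading without settling it.
- **Aim 1 is invalid.** The pooled effect averages two versions of the VCI, but it remains a valid effect of the packages delivered.

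**Conclusion.** The concern holds for the interpretation of Aim 2. On the VCI-only reading, the ethnicity interaction estimates δ + γ and cannot be split by any analysis. This part is certain given that reading, and it would change only if the content also goes to groups where it is not now described.

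The size of the distortion is unknown. Extra contact lies between about 3% and 25% depending on a frequency that the plan does not give, and the documents give no effect for the content. The 12% rejection rate shows what an assumed 1-point effect would do under the stated simplifications. It is not a forecast, and the direction of bias could be either way.

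**What to change.** 1. State in Aim 2 and in the analysis section that the Hispanic/NED contrast compares VCI plus added content with VCI, and that a difference, or its absence, will not be attributed to ethnicity.
2. Reconcile Group VCI Sessions, UPLIFT Manualized Program and Procedures performed for research purposes only, so that they agree on which arms receive the content, how often, and whether it is added to the hour. The AC descriptions should say explicitly whether it applies there.
3. Record the session minutes delivered, by group, in both arms.

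The cost is wording, a simple log, and a narrower Aim 2 claim.

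Whether the content is also given in AC is a design choice for the sponsor. If it were, the interaction would become δ + (γ in VCI − γ in AC). That removes the confounding only if the content has the same effect with and without UPLIFT, that is, if the two are additive. It would also put mental health discussion into the control arm.
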